17.0 Statistical Considerations

17.1 Data Analysis Plan:

Analysis of Specific Aims 1-3

Data available at baseline, 4 months, 8 months, and 12 months will allow for individual growth curve models that examine change in ADRD caregiver outcomes.^{103,104} Multilevel analysis approaches are available that support growth curve modeling. In this context, growth curve modeling is an example of a 2-stage modeling process consisting of 1) a within-subjects model across time, and 2) a between-subjects model that incorporates caregiver and person with ADRD covariates.^{105,106} The primary independent variable in the proposed investigation consists of an indicator variable for random assignment into the RCTM treatment condition or the attention care control. [SAS (version 9.4) Proc Mixed¹⁰⁷] will be used to conduct these analyses, as it supports multilevel and growth curve modeling procedures.

Our proposed analyses will provide in-depth tests of Specific Aims 1 to 3 (i.e., rates of change in primary subjective stress, secondary role strains, residential care stress, and caregiver depressive symptoms) over a 12-month period. In one set of outcome evaluations, the baseline value will be included as a covariate, and time will be “centered” at 4-months post-baseline. This scales the intercept effect to be a main effect of RCTM group assignment and allows the RCTM treatment and the attention control groups to have different 4-, 8-, and 12-month change trajectories, or an RCTM treatment*time interaction effect. After establishing that the individual growth parameter estimates have significant variance around the mean trajectories of change in key dependent variables, an RCTM treatment vs. control group indicator will be added as the key independent variable to predict intercepts and rates of change in outcomes. Additional analyses will determine if covariates (e.g., context of care indicators, primary objective stressors, and resources) significantly vary across the RCTM treatment and control groups at baseline and over time via growth curve modeling procedures. If statistically significant variations between the RCTM treatment and control groups are found, initial status and rate of change parameters for these covariates will be included in all tests to provide further statistical control.

SOCIAL PROTOCOL (HRP-580)

PROTOCOL TITLE: The Residential Care Transition Module

VERSION DATE: 2/10/2022

Secondary Analyses

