Intensive longitudinal analysis procedures (multilevel regression analyses of outcome and growth curve modeling) will be utilized to capitalize on the randomized controlled design and the multiple waves of data to be collected. The number of ADRD caregivers to be enrolled to address study hypotheses was determined using power analysis procedures that take into account the hierarchical analytic design of the study.⁹⁹ In this framework, the researcher identifies the Type I error rate (e.g., $p < .05$) to differentiate between a null and alternative test hypothesis, a suitable level of statistical power (.80 is considered an excellent power value), and the expected difference between the two study groups in order to determine the number of ADRD caregivers to enroll into the project. [We sought a sample size that would be sufficient to detect a group difference of 0.50 standard deviation units and modest effect sizes that we identified in our preliminary efficacy trial. This is considered to be a “medium” effect size¹⁰⁰ and is a reasonable benchmark to evaluate the efficacy of a behavioral intervention in comparison to a usual care control condition. We also used a Bonferroni adjusted Type I error rate of .0125 (.05/4) to accommodate up to 4 primary outcome variables (primary subjective stress; secondary role strain; residential care stress; caregiver depressive symptoms), and we allowed for a conservative 10% loss to follow-up. With these specifications, an enrolled sample size of 240 ADRD caregivers (120 in each group) was sufficient to provide adequate statistical power. After attrition, this sample size will give us .87 power to detect a 0.50 effect size and .80 power to detect a slightly smaller effect size of 0.46 standard deviation units. This effect size could apply to covariate-adjusted mean differences at a particular follow-up point, or two linear slope differences of change across time between the intervention and control conditions.]

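### Section 17.1 names no multiplicity rule; Holm's step-down would keep the 5% family-wise bound used for sizing and give more power than single-step Bonferroni when several effects are real

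*Combined protocol and SAP*

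**What the plan says.** The only text on multiplicity is in Section 17.2 (Power Analysis, Determination of Sample Size): "We also used a Bonferroni adjusted Type I error rate of .0125 (.05/4"). The stated purpose is "to accommodate up to 4 primary outcome variables (primary subjective stress; secondary role strain; residential care stress; caregiver depressive symptoms"). With 10% loss to follow-up, the section concludes that "an enrolled sample size of 240 ADRD caregivers (120 in each group) was sufficient to provide adequate statistical power", and that after attrition "this sample size will give us .87 power to detect a 0.50 effect size", with .80 power at 0.46 SD.

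Section 17.1 describes growth curve models for Aims 1 to 3 and says "Our proposed analyses will provide in-depth tests of Specific Aims 1 to 3". It gives no significance level, no adjustment and no order of testing. Section 17.3 only refers back to it. Section 17.2 mentions an error rate once more, as a general illustration: "the researcher identifies the Type I error rate (e.g., $p < .05"). Sidedness is not stated.

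Two other places matter. Section 3.1 names primary subjective stress and negative mental health outcomes as primary. Section 3.2 places secondary role stressors and residential care stress among the secondary outcomes and lists caregiver depressive symptoms with the other variables. Section 17.1 also lets treatment predict both an intercept (a main effect, with time centred at 4 months) and a rate of change, so each outcome can yield two treatment tests.

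**The concern.** Section 2.3 predicts benefit in every domain of the four-outcome family. If .0125 carries over from sizing to analysis, every outcome must clear .0125 however strong the others are. Holm's procedure compares the ordered p-values with .05/4, .05/3, .05/2 and .05, stopping at the first failure. It gives the same family-wise protection with lower hurdles after the first rejection, and it needs no more participants and no ranking of the outcomes. If .0125 does not carry over, 17.1 has no rule at all. One sentence in 17.1 deals with either case. At stake is power for the second and later outcomes across Aims 1 to 3, at a fixed sample size.

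**Working it through.** **Inputs.** From 17.2: 240 enrolled, 10% loss, up to four outcomes, alpha .05/4 = .0125, effects of 0.50 and 0.46 SD (SD = 1). From 5.2: 1:1 allocation. Analysed per arm: 240 × 0.90 / 2 = 108. Assumed: two-sided tests, and equal pairwise correlation between the outcome test statistics.

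**Reproducing the plan's power.** Power ≈ Φ(d√(n/2) − z), with √(108/2) = √54 = 7.348 and z = 2.498 for two-sided .0125.
- d = 0.50: 3.674 − 2.498 = 1.177, power .880 (noncentral t, 214 df: .875). Stated: .87.
- d = 0.46: 3.380 − 2.498 = 0.883, power .811 (noncentral t: .805). Stated: .80.

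One-sided tests would give .924 and .873, which do not match. The stated figures are therefore correct for two-sided tests at .0125.

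**Why Holm keeps the bound.** If m of the nulls are true, the first true null that Holm rejects must have p ≤ .05/m. By the Bonferroni inequality, the chance that any of m true nulls has p that small is at most m × .05/m = .05, whatever the correlation. Each Holm threshold is at least .0125, so Holm never loses a Bonferroni rejection.

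**Single-test power at the Holm thresholds**

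| Threshold | .0125 | .0167 | .025 | .05 |
|---|---|---|---|---|
| d = 0.50 | .880 | .900 | .924 | .957 |
| d = 0.46 | .811 | .838 | .873 | .922 |

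Holm's power per outcome must lie between the first and last columns.

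**Simulation.** Normal test statistics with mean 7.348 × d, 400,000 draws per setting, 108 per arm, correlation .3 to .7, real effects 0.46 SD unless stated:

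| Setting | Bonferroni | Holm |
|---|---|---|
| Four of four real, power per outcome | .81 | .875–.89 |
| Two of four real, power per real outcome | .81 | .83 |
| One of four real, power for that outcome | .81 | higher by about .001 |
| Effects .46/.46/.30/.30 (correlation .5), power for each smaller effect | .38 | .52 |
| Family of two, both real, power per outcome | .87 | about .91 |
| Four of four real, chance of at least one rejection | .94–.99 | identical |

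With all four effects at 0.50 SD, power per outcome goes from .88 to .93–.94. With independent outcomes, the all-real gain at 0.46 SD is slightly larger (.81 to .90).

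**Error check.** The highest simulated family-wise error under Holm was .049, and no draw had a Bonferroni rejection that Holm missed. Holm uses more of the allowance when some nulls are true: with two of four effects real at 0.50 SD and independent outcomes, family-wise error goes from .025 to .046, still within .05.

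**The case against.** A reader might infer that the trial is committed to testing every outcome at .0125 and so wastes power on Aims 1 to 3. The documents do not say that. The figure stands under sample-size determination, and 17.1 never adopts it as a decision rule. Nor is it an error: Bonferroni is valid, and under it each outcome already reaches the plan's .80 target at 0.46 SD. Both objections stand and limit this to an efficiency point.

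It is also tempting to quote the chance of showing all four effects, which rises from .52–.64 to .75–.80 at 0.46 SD. The protocol sets no such success criterion, so that figure should not carry the argument. The per-outcome gain depends on how many effects are real and is close to nil if only one is. This stands too.

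Holm also cannot be applied until the family is fixed and each outcome has one p-value. Section 3 and 17.2 disagree on the family, and 17.1 allows two treatment tests per outcome. That is true, but Bonferroni has the same need, so it belongs in the fix and is no reason to prefer single-step testing.

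Timing is a fair caution. This version is dated 2/10/2022, after the parent project's planned end of 05/31/2021 in Section 8.1. Section 17.1 leaves interim analyses possible, and 20.2 includes review of interim data for efficacy. The documents do not show whether outcomes have been seen by arm. A less strict rejection rule is credible only if it is fixed before that happens.

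**Conclusion.** The point holds as a low-cost improvement. Section 17.1 lacks a multiplicity rule, and Holm is uniformly at least as powerful as the single-step Bonferroni used in 17.2, at the same 5% family-wise bound and the same 240 participants. At 0.46 SD the gain per outcome is about 6 to 8 points if all four effects are real, about 2 points if two are, and about 0.1 point if one is. If the family is only two outcomes and both effects are real, it is about 4 points. The chance of at least one significant outcome is unchanged, because the smallest p-value faces the same threshold under both methods.

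These sizes rest on 108 analysed per arm, two-sided tests and an assumed correlation of .3 to .7. Holm's error control rests on none of the correlation assumptions.

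**What to change.** Before outcome data are examined by arm:

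1. State in 17.1 that the primary family is tested by Holm's step-down procedure at family-wise two-sided .05.
2. Reconcile Section 3 with 17.2, so that the same outcomes are called primary in both and the number in the family is fixed.
3. Name in 17.1 the one treatment-effect p-value per outcome that enters the procedure: either the intercept (main) effect or the treatment-by-time effect.
4. Keep .0125 in 17.2, described as the worst-case planning alpha for a family of four. The sample size does not change.

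The Holm rule itself is one sentence. Items 2 and 3 take a decision by the team, which any multiplicity rule would require. The small downside is that simultaneous confidence intervals matching Holm are less direct than Bonferroni intervals. The plan specifies none, so unadjusted 95% intervals, labelled as such, can be reported beside Holm-adjusted p-values.

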Following feasibility testing and refinement of the treatment manual, a pilot efficacy evaluation of the RCTM intervention was conducted.⁹¹ A randomized controlled design was used ($N = 36$; $n = 19$ in usual care control condition; $n = 17$ in the RCTM treatment condition); participants were administered a pre-RCTM baseline survey along with 4- and 8-month follow-up interviews. Participants had admitted their relatives to a RLTC an average of 141 days prior to the baseline interview. Twenty-nine caregivers were women and 17 were spousal caregivers; all were Caucasian. On average, caregivers were 62.67 years of age and had provided care an average of 51.79 months. All RCTM counseling sessions provided emotional support to participating caregivers. Twenty-six (29.6%) individual and three (33.3%) family counseling sessions addressed relatives' behaviors. Approximately 40% of all individual sessions addressed caregivers' issues with the relative's facility compared with only one family session. Bivariate analyses of sociodemographic characteristics, caregiving duration, and other context of care indices found no statistically significant differences between the RCTM treatment and control conditions. Seven care recipients had died during the 8-month follow-up; 5 prior to the 4-month interview and 2 prior to the 8-month interview. Analyses of variance found that caregivers in the RCTM treatment group indicated significantly less distress on the Neuropsychiatric Inventory-Questionnaire⁹² at 4-month follow up compared to caregivers in the control group ($p < 0.05$). Caregivers in the RCTM treatment group reported less role overload at 8 months compared to usual care controls ($p < 0.05$). Due to the small pilot sample, a number of findings did not achieve statistical significance below the $p < 0.05$ threshold but trended in the expected clinical direction ($p \leq 0.10$; role overload at 4 months; Perceived Stress Scale at 4 months;⁹³ and Zarit Burden Inventory⁹⁴ at 8 months). Focus groups conducted following the RCTM indicated that caregivers highly valued the readily available psychosocial support following RLTC placement. Combined, the preliminary quantitative and qualitative data emphasize that the provision of skilled psychosocial support can potentially help families navigate the emotional distress and crises in the months following a cognitively impaired relative's admission to RLTC.⁹¹

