3.0 Study Endpoints/Events/Outcomes

3.1 Primary Endpoint/Event/Outcome:

- The parent study's primary outcomes include reductions in family members' primary subjective stress and negative mental health outcomes.
- The administrative supplement's primary outcomes include changes in caregivers' mental health and caregiving stress before and during the COVID-19 pandemic.

3.2 Secondary Endpoint(s)/Event(s)/Outcome(s):

- Parent study's secondary outcomes include secondary role stressors, and residential care stress. Other variables include context of care, caregiver depressive symptoms, primary objective stressors and resources.
- The administrative supplement's secondary outcomes include AD/ADRD caregivers' and care recipients' COVID-19 related experiences and resilience during COVID-19 pandemic.

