survey may be sent together per study procedures. The follow-up survey is scheduled to be sent 4 months (+/- 7 days) following the receipt of the previous survey or within 7 days of receiving the disposition status. If the date a survey is scheduled to be sent falls on a weekend/holiday, the survey send date is moved to the next business day (and the survey is sent +/- 7 days from that date). Participants are given several reminders to facilitate survey completion. *[Please note: Survey time-points are calculated following the date of receipt of the previous survey (or if the previous survey was not returned, surveys time-points are calculated using the appropriate time interval following the receipt date of the prior survey). Based on this, if participants are not prompt in survey completion, subsequent surveys are pushed back accordingly.]* In addition to the 4, 8, and 12-month surveys, additional surveys may be sent if the participant is participating in surveys related to the COVID supplement. These supplemental survey time points are calculated according to the protocol-based survey schedule (i.e. 1, 3 months) following the sent or receipt date of the previous survey as described above. Data will be collected regarding any caregiver status changes or bereavements. Surveys will continue to be administered whether the person with ADRD moves to another setting or passes away. A modified survey will be administered if the person with ADRD passes away during the course of the study. For participants still enrolled in the RCTM study in May 2020, additional COVID-19 related questions will be included in follow-up surveys.

Note: Depending on the survey type and time-point, the due date for surveys administered to primary caregivers that enrolled with other family members is either calculated separately or is dependent upon the receipt of the other family members' surveys. Specifically, due dates for treatment fidelity surveys and routine 4-month surveys are calculated based upon the receipt of the previous survey time-point by all family members; other surveys are calculated based upon the receipt of that individual's survey only.

We will take several steps to address attrition bias. If ADRD caregivers wish to withdraw from the RCTM treatment group, but agree to continue with follow-up interviews/surveys, we will continue routine data collection without counseling.

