9.0 Study Population

9.1 Inclusion Criteria: Eligibility criteria include family caregivers who consider themselves the most involved in visiting and providing assistance to the person with memory loss (or who share the primary caregiving role equally). For the caregiver to participate, the care recipient must be residing in a RLTC setting (e.g. assisted living, nursing home, memory care, or other residential long-term care setting) and have received a physician's diagnosis of ADRD. Family caregivers must be English speaking, 21 years of age or older, and not participating in any other one-to-one psychosocial consultation specifically for caregiving (support group participation is not a deterrent to enrollment, nor is general counseling not specific to caregiving). Family caregivers on psychotropic medications, such as anti-depressants or anti-psychotics, will be eligible if they have remained on a stable dosage for the last 3 months.

The sample for the administrative supplement focused on COVID-19 will be drawn from participants in the original RCTM parent study. Caregivers who have already completed the study and who have not previously reported bereavement, as well as those caregivers who remain currently enrolled in the parent study, will be invited to take part in the proposed supplemental assessments. Among previously-completed participants, those whose care recipient is still alive will be eligible to re-enroll. Among currently-enrolled participants, any who are not bereaved, or who are bereaved but have been continuing to participate in

SOCIAL PROTOCOL (HRP-580)**PROTOCOL TITLE: The Residential Care Transition Module****VERSION DATE: 2/10/2022**

bereavement-modified surveys, will be eligible to participate in supplemental surveys. Both control and treatment group participants will be eligible. Previously-completed caregivers whose care recipient has already passed away will not be eligible to enroll in the supplement.

9.2 Exclusion Criteria: Caregivers are not eligible to participate if they do not meet the inclusion criteria above.

9.3 Screening: If caregivers are interested in participating, the RC will conduct a brief screening procedure using the RCTM Screening Form, developed on the above eligibility criteria.

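### Do secondary role strain and residential care stress need a stated rule, and a lower power figure, for the time after the relative dies?

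*Combined protocol and SAP*

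**What the plan says.** Section 17.2 names four outcomes (primary subjective stress, secondary role strain, residential care stress, depressive symptoms), divides .05 by 4, and states: "we allowed for a conservative 10% loss to follow-up". With 240 enrolled it reports power of .87 for 0.50 SD and .80 for 0.46 SD. On what that effect means, it adds: "This effect size could apply to covariate-adjusted mean differences at a particular follow-up point, or two linear slope differences of change across time".

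Section 17.1 fits growth curve models in SAS Proc Mixed. In one set of analyses, baseline is a covariate and time is centred at month 4. Of that centring it says: "This scales the intercept effect to be a main effect of RCTM group assignment". Neither section mentions the relative's death.

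Other sections do. On the pilot, 2.2 reports: "Seven care recipients had died during the 8-month follow-up; 5 prior to the 4-month interview and 2 prior to the 8-month interview". On follow-up, 5.3 says: "Surveys will continue to be administered whether the person with ADRD moves to another setting or passes away", and "A modified survey will be administered if the person with ADRD passes away during the course of the study". It also provides for recording bereavements. Section 9.1 refers to the same instrument when it says which enrolled caregivers may join the COVID-19 supplement: those who have continued with "bereavement-modified surveys, will be eligible to participate in supplemental surveys". The scales kept in that survey are not listed.

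Section 3.2 ranks two of the four outcomes differently from 17.2: the parent study's "secondary outcomes include secondary role stressors, and residential care stress".

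**The concern.** Section 1.1 describes secondary role strain as how the relative and the caregiver have adjusted to the placement. It describes residential care stress through dealings with staff, distress about the placement and friction in the facility. Much of this has no referent once the relative has died, whereas depressive symptoms can still be reported. Bereaved caregivers stay in the study, so they are not part of the 10% loss, yet they may have no meaningful score on these two scales.

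Two things would be at stake. A 12-month effect could describe all caregivers or only those whose relative is alive, and the choice could be made after the results are known. And if pilot mortality carries over, the single .87/.80 would be too favourable for these two outcomes at later time points.

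**Working it through.** **1. The plan's figure.** Inputs from 17.2: two-sided level .0125 (sidedness is not stated, but only two-sided reproduces the figures), 120 per arm, 10% loss, so N = 240 × 0.90 = 216. Two-sample power uses the noncentral t with N − 2 degrees of freedom and noncentrality d√(N/4).
- d = 0.50: 0.50 × √54 = 3.674, power .875.
- d = 0.46: 0.46 × √54 = 3.380, power .805.

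The stated .87 and .80 are right.

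**2. Deaths in the pilot (2.2).** Before month 4: 5/36 = 13.9%. Before month 8: 7/36 = 19.4%, exact 95% interval 8.2% to 36.0%. Month 12 was not observed. Repeating the month-4-to-8 experience gives 1 − (29/36)(29/31) = 24.6%; a constant hazard gives 1 − (29/36)^1.5 = 27.7%.

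**3. One time point, assuming no usable score after death.** N = 240 × (1 − deaths) × (1 − other loss), d = 0.50:

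| Month | N, deaths alone | Power | N, plus 10% loss | Power |
|---|---|---|---|---|
| 4 | 207 | .857 | 186 | .811 |
| 8 | 193 | .829 | 174 | .779 |
| 12 (24.6%) | 181 | .798 | 163 | .746 |
| 12 (27.7%) | 174 | .778 | 156 | .724 |

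Section 5.4 reports survey completion above 98% per wave, so other loss nearer 2% is plausible; month 8 is then .820. At 0.46 SD, month 8 from deaths alone is .750. At the ends of the pilot interval, power from deaths alone at 0.50 SD is .882 and .715.

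**4. The model in 17.1.** A growth model also uses scores from before death. I took months 4, 8 and 12, a linear trend with time centred at month 4, compound symmetry with correlation .3, .5 or .7, missing values from death onward (27.7% by month 12) and no baseline covariate. Power = Φ(0.50/SE − 2.498).
- Group effect at month 4, deaths alone: .88 to .90 (correlation .5: SE .1337, 3.740 − 2.498 = 1.242, power .893).
- Group effect at month 4, plus 10% loss at every wave: .84 to .87 (correlation .5: SE .1409, power .853).
- The same model with only the plan's 10%: .90 to .92.
- Model-based month-12 contrast, plus 10% loss: about .81 (correlation .5: SE .1484, power .809).
- Slope difference, sized so that the plan's 10% gives .875: .80 to .83 from deaths alone, .75 to .79 with the further 10%.

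**5. Scales kept, but the treatment difference ends at death.** At month 8 the effect becomes 0.50 × 29/36 = 0.403 SD. Power is .726 with N = 240 and .670 with N = 216.

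**6. A factor in the other direction.** If 0.50 is in unadjusted SD units, which 17.2 leaves open, adjustment for a baseline correlated .5 with follow-up divides the SD by 1/√(1 − .25) = 1.155. Month 8 from deaths alone rises to .931. If 0.50 is already adjusted, nothing is gained.

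**7. Status of the outcomes.** The level in 17.2 gives 4 × .0125 = .05 across all four outcomes, whichever of them are called primary.

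**The case for a change.** The strongest case is about meaning. The plan foresees bereavement in its procedures, yet its analysis section is silent, and these are the outcomes where death matters most. The 10% cannot simply be read as covering deaths, because bereaved caregivers are still surveyed. Completion above 98% concerns surveys returned, not whether a scale still applies. Section 17.2 itself offers its effect size for later time points and slopes, where the information thins out. A few lines of text would cost little.

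Much of this stands. The rule is absent, one power figure covers four outcomes, and 3.2 and 17.2 disagree on status. A report on Aims 2 and 3 will have to say whom the 12-month effect describes.

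What does not follow is that the plan needs the change. An instruction to analyse these outcomes while the relative is alive, using values up to death and leaving later model values uninterpreted, would not alter the Proc Mixed coefficients being tested; fitted to the same pre-death values, the slope and month-12 terms are the same. A rule limited to these two outcomes would also be incomplete, since the conceptual model in section 2.3 places closeness to the relative, and difficulty with the relative's mental state, within primary subjective stress. Quoting power at 25% or 30% missing as pilot-based would overstate the pilot, which observed 19.4%. Lastly, recruitment in the 8.1 timetable ends by project month 55, which is December 2020 counting from June 2016, and this version is dated February 2022. Restating design power would change neither N nor any observed confidence interval.

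**Conclusion.** This is a gap that analysts can fill sensibly, not an error in the plan. The .87/.80 is correct arithmetic, and the documents do not show it to be wrong for these two outcomes. The group effect described in 17.1 stays above .80 in every growth-model case above in which post-death scores are missing. At 0.50 SD, a single comparison stays above .80 at pilot mortality through month 8 (.86 and .83 from deaths alone). It falls below when 10% other loss is added at month 8 (.78), at the extrapolated month 12 (.72 to .80), or if the effect is taken to end at death (.73 or .67 at month 8). The slope difference is the most exposed part of the model, at .75 to .83.

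Those lower figures depend on assumptions the documents cannot settle: that the modified survey yields no usable score, or that the effect stops at death; and that a 36-person pilot, enrolled on average 141 days after admission, predicts mortality here.

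Surveys continue after death and bereavements are recorded, so the data allow analysis up to death, comparison by bereavement and reporting by arm. The mismatch in outcome status is a labelling slip: dividing by 4 already covers all four outcomes.

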As noted in various recommendations for mixed methods sampling, 30-40 participants is considered an adequate sample size for semi-structured interview protocols as proposed here.^{101,102} As “sample size” in qualitative research is based more on the richness and depth of open-ended data collected, it is possible to achieve the goals of the post-randomized controlled evaluation embedded component with a smaller number of semi-structured interviews. Given the expected number of ADRD caregivers in the RCTM treatment condition, we decided on 30 semi-structured interviews to ensure the richness of the qualitative data collected.

17.3 Statistical Analysis: Please see data analysis plan.

17.4 Data Integrity: Several steps will be taken to ensure data quality. The psychometric properties of the study measures are generally well-established; however, additional steps will be taken to ensure the reliability and validity of the study measures. For example, internal reliability will be established with Cronbach's alpha (α) estimates for each measure and subscale. These procedures will help to establish the psychometric qualities of each tool beyond their utilization in prior study. Each outcome variable will be examined to determine if skewness exists or outliers are present. Normal probability plots and histograms of each

SOCIAL PROTOCOL (HRP-580)**PROTOCOL TITLE: The Residential Care Transition Module****VERSION DATE: 2/10/2022**

dependent variable will be analyzed; this step is necessary because individual outcome variables must have near-normal distributions in order to be included in subsequent models. If the outcome variables are not normally distributed, the original variables can be subjected to algebraic transformations or other standard transformation techniques to meet model assumptions.

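### Section 17.4 tests the raw outcome for near-normality instead of the residuals and random effects, so it can trigger a needless transformation that changes a primary estimand

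*Combined protocol and SAP*

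**What the plan says.** Section 17.4 begins with inspection: "Each outcome variable will be examined to determine if skewness exists or outliers are present", using plots of each dependent variable. The reason given is that "individual outcome variables must have near-normal distributions in order to be included in subsequent models". For an outcome that fails, "the original variables can be subjected to algebraic transformations or other standard transformation techniques to meet model assumptions".

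The section gives no threshold for near-normal, names no transformation, and does not place the inspection before or after unblinding. It does not require the data to be pooled or blinded to arm. It keeps no original-scale analysis and has no rule for a transformation that fails.

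The outcome model is in section 17.1: growth curves fitted in "SAS (version 9.4) Proc Mixed". "In one set of outcome evaluations, the baseline value will be included as a covariate", with time centred at 4 months and a treatment-by-time interaction allowed. That section mentions neither the distribution of residuals nor that of the random effects, and it does not fix the outcome scale.

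Section 17.2 sizes the trial to "detect a group difference of 0.50 standard deviation units" at a Bonferroni level of .0125, allowing for as many as four primary outcomes. Section 3.1 lists only two domains as primary. The rule in 17.4 covers every outcome variable, so it reaches the primary outcomes on either list.

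**The concern.** A linear mixed model makes its normality assumption about the residuals and random effects, conditional on the covariates. It makes none about the marginal distribution of the outcome. An outcome can be plainly skewed because a covariate such as its own baseline is skewed, while the model fits well. The reverse can also occur. A rule that looks only at the outcome can raise an alarm when nothing is wrong with the model.

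The alarm has consequences. Section 17.2 says that the effect may be a covariate-adjusted difference in means or a difference in linear slopes. After a log or root transformation, neither is a difference in scale points any longer. Two primary outcomes could end up on different scales, each chosen after the data were seen, with no original-scale estimate to fall back on.

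**Working it through.** **1. Inputs.** From section 17.2: 240 enrolled, 120 per arm, 10% loss, so 120 × 0.9 = 108 per arm; α = .05/4 = .0125; effects 0.50 and 0.46 SD. Sidedness is not stated. The documents give no SD, skewness or correlation for any outcome, so the distributions in steps 3 and 4 are assumptions.

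**2. The plan's power.** With a normal approximation and a two-sided test, power = Φ(d√(n/2) − z), where z = 2.498 for α = .0125 and √(108/2) = 7.348.

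- d = 0.50: Φ(3.674 − 2.498) = Φ(1.176) = .880
- d = 0.46: Φ(3.380 − 2.498) = Φ(0.882) = .811

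The noncentral t gives .875 and .805. Both versions agree with the stated .87 and .80 to within about a point. A one-sided test would give .924 and .873, so the plan's figures are two-sided. Nothing in this calculation depends on the diagnostic rule.

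**3. Does the stated check look at the right quantity?** Assume a baseline x that is exponential (variance 1, skewness 2), an outcome y = 0.8x + 0.6e with e standard normal, and no treatment effect. The outcome has variance 0.64 + 0.36 = 1 and skewness 0.8³ × 2 = 1.02. The residuals given x are exactly normal. With 108 per arm, ANCOVA on baseline and 2,000 trials:

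- Shapiro-Wilk at 5% on the outcome: flagged in 98.2%
- Shapiro-Wilk at 5% on the residuals: flagged in 4.3%, about the nominal rate
- type I error of the untransformed analysis: .012 against .0125 (Monte Carlo standard error √(.0125 × .9875/2000) = .0025)

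Repeat runs under similar assumptions flagged the outcome in 98% to over 99% of trials and the residuals in 4% to about 6%, with type I error from .011 to .015. A check of the outcome would nearly always call for a transformation that the model does not need.

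**4. Does choosing the scale by shape inflate type I error?** Assume log-normal baseline and outcome (log-SD 0.5 or 0.8, log-scale correlation 0.6), no treatment effect, and 10,000 trials (Monte Carlo standard error .0011). The shape rule takes whichever of raw, square root and log has the least pooled skewness.

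| Analysis | log-SD 0.5 | log-SD 0.8 |
|---|---|---|
| Raw scale | .0130 | .0116 |
| Scale chosen by pooled shape | .0139 | .0129 |
| Smallest p-value of the three scales | .0196 | .0198 |

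With a gamma outcome of skewness 1.4 and 20,000 trials, transforming when pooled skewness exceeded 1 gave .0125 (log) and .0122 (square root). Choice by shape therefore stays at about .012 to .014. Only choice by result inflates the error.

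**5. What does a transformation do to the estimand?** Let C(t) be the control trajectory and suppose the treated trajectory is k·C(t), with k constant after month 4. On the log scale the arms differ by log k at every visit, so the treatment-by-time interaction is zero. On the original scale the slopes differ by (k − 1) times the control slope, which is not zero unless k = 1 or the control trajectory is flat. The same data can show an interaction on one scale and none on the other.

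**The case against.** The strongest defence is that looking at distributions is routine, that the stated purpose of transforming is to satisfy the model's assumptions, and that the text sits under Data Integrity and not in the analysis plan. A competent analyst would look at residuals anyway. This does not remove the point. The text makes the outcome's own distribution the entry condition, and no other section supplies a residual check or fixes the scale.

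Several stronger conclusions are tempting, and here the defence is right.

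- A reader might infer that the rule inflates type I error to about .016 to .020. Those figures come from picking the scale with the smaller p-value. The plan chooses on histograms, probability plots, skewness and outliers, and the treatment comparison plays no part.
- A reader might infer that a skewed primary outcome would be dropped. The sentence that follows offers transformation; nothing says that an outcome is excluded.
- A reader might infer that the power calculation is undermined. The target is in standard deviation units, not points on an instrument, so it can be read on any scale, and the stated power reproduces.
- A reader might take it as given that depressive symptoms will be skewed, or that empirical standard errors must be mandatory. The documents give no skewness, and the untransformed model-based analysis held its level in these runs.

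One limit also stands: the simulations use a single follow-up with ANCOVA. The random-effects growth model over 4, 8 and 12 months was not simulated.

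**Conclusion.** The point holds as a defect in the diagnostic rule and in pre-specification. Section 17.4 inspects the wrong quantity for the model in section 17.1, and its open-ended remedy can change the estimand of a primary outcome when the model has no fault. Under one assumed configuration, the outcome would be flagged in about 98% of trials and the residuals in about 4%.

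There is no material type I error problem if the choice is made on pooled shape: about .012 to .014 against .0125. I read the inspection as pooled over arms because the text never mentions arm, but the plan does not say so. Sample size and power are unaffected. The simulated figures rest on assumed distributions. The argument about which quantity the model's normality assumption concerns does not.

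**What to change.** Replace the near-normality condition and the transformation sentence in section 17.4 with:

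> Primary outcomes are analysed on their original scale. Model residuals and random effects, not marginal outcome distributions, are checked. If they are clearly non-normal, robust (empirical or bootstrap) standard errors or a transformation named in advance, chosen on pooled data blinded to arm, are reported as a sensitivity analysis.

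Section 17.1 should refer to this text so that the scale is fixed where the model is defined. The cost is a few sentences. The downside is a possible small loss of efficiency if the residuals of an outcome prove very skewed. N = 240 and the stated power of .87 and .80 stay as they are.
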